5.6.8. Pregnancy Test Analyses

Urine pregnancy test is taken at screening, prior to every treatment (initial and touch-up), and study exit. Participants with a positive result for the Safety Population throughout the study period will be presented as a listing.

5.8. Interim Analyses

No interim analysis is planned for this study.

6. Supporting Documentation

JUVÉDERM® VOLUMA® with Lidocaine

6.1. Appendix 1: List of Abbreviations

3D 3-dimensional AE adverse event

ATC Anatomical Therapeutic Chemical

BOCF baseline value carry forward

CI confidence interval

CP control period

eCRF electronic case report form

EI Evaluating Investigator

GAIS Global Aesthetic Improvement Scale

IES Intercurrent event(s) strategy

ISR injection site response

LS least square

MedDRA medical dictionary for regulatory activities

mITT modified intent-to-treat

NSS Nose Satisfaction Scale

PCP Post-Control period

PLS Population-level summary

PP per-protocol

SAE serious adverse event SAP statistical analysis plan

SE standard error

SOC system organ class

TEAE treatment-emergent adverse event

TP treated period

Tx treatment

VITP voluma initial treated population

VOTP voluma optionally treated population

WHO World Health Organization

JUVÉDERM® VOLUMA® with Lidocaine

6.2. Appendix 2: Changes to Protocol-Planned Analyses

In this SAP, the primary analysis will be done by an MMRM. The original primary analysis in Protocol 1894-701-008 Amendment 1 was based on observed data. The original analysis based on observed data will be included as one of the sensitivity analyses.

The definition of mITT is changed from "Subjects who are randomized to study treatment, receive at least 1 study device treatment and complete at least 1 effectiveness assessment (Treatment Group); and subjects who are randomized to no treatment and complete at least 1 effectiveness assessment (Control Group)" in protocol to "All participants who are randomized and have at least 1 assessment of change from baseline in nose volume" in SAP. The changes make it clear that participants need to have at least one primary effectiveness variable (purpose of effectiveness assessment). Participant who are randomized to treatment but don't receive study device treatment will be withdrawn from the study and have no any follow-up visits. So device treatment requirement was not necessary and excluded from definition in SAP for simplicity.

The definition of PP is changed from "All mITT subjects who do not have any significant protocol deviations affecting the primary effectiveness endpoint" in protocol to "All mITT participants who have baseline and Week 24 assessments of change from baseline in nose volume and do not have any significant protocol deviations affecting the primary effectiveness endpoint" in SAP. This change adds one requirement for the availability of primary endpoint in line with key criteria of PP definition in ICH E9.

6.3. Appendix 3: Supporting Study Information

6.3.1. Demographics

Demographic parameters (age [years]; sex; race [Asian]; ethnicity [Chinese]) will be summarized descriptively by treatment group for the mITT populations. Age (years) were calculated relative to informed consent date.

6.3.2. Baseline and Disease Characteristics

Baseline characteristics including weight, height, and body mass index will be summarized descriptively by treatment group for the mITT population.

6.3.3. Protocol Deviations

Significant protocol deviations will be identified. Unique participants reporting significant protocol deviations will be summarized in total and by treatment group for all randomized participants as described in Table 6-1.

Listing of significant protocol deviations will be provided.

JUVÉDERM® VOLUMA® with Lidocaine

Table 6-1 Protocol Deviation Summary

| Endpoint | Description | Timing | Methodology |
|----------------------|--|--------------|--------------|
| Significant protocol | Number (%) of participants with significant protocol | During study | Categorical |
| deviations | deviation will be summarized (All randomized) | period | descriptives |

6.3.4. Medical History

Abnormalities in participants' medical, surgical, cosmetic and dental history, encompassing abnormalities, surgeries, and procedures reported as occurring before the Screening Visit, will be coded using MedDRA, version 21.0 or newer. Listing will be provided for the mITT population.

6.3.5. Prior/Concomitant Medications

Medications will be coded using the WHO Drug Dictionary, version March 2017 or newer. Unique participants who reported medications (Anatomical Therapeutic Chemical [ATC] 4 class and PT) will be summarized. Prior medication will be summarized by treatment group and total for screening period based on mITT Population. Concomitant medication will be summarized by treatment group for CP using the mITT Population, for TP using VITP VOTP as described in Table 6-2.

Table 6-2 Prior and Concomitant Medications

| Endpoint Description | | Timing | Methodology |
|-------------------------|---|-----------|--------------------------|
| Prior medications | Medications taken before the study treatment by treatment group and in total (mITT) | Screening | Categorical descriptives |
| Concomitant medications | Medications taken during the corresponding period | CP, TP | Categorical descriptives |

6.4. Data Handling Convention

6.4.1. Analysis Window

6.4.1.1. Effectiveness

Most recent treatment refers to initial treatment if touch-up is not performed, otherwise touch-up treatment. The reference day is defined for each group and each study period. The analysis visit windows for effectiveness endpoints are defined in Table 6-1 for the treatment group and in Table 6-2 and Table 6-3 for the control group. If more than 1 measurement exist in one visit, the measurement that close to the target date of the visit will be used for summary analysis. If both measurements have the same time interval to the target date, the later one will be used for summary analysis. But all measurements will be listed in data listings

If analysis date ≥ reference date, then
Analysis day = analysis date – reference date + 1

If analysis date < reference date, then
Analysis day = analysis date - reference date

JUVÉDERM® VOLUMA® with Lidocaine

Table 6-3 Effectiveness Analysis Visit Definitions for Treatment Group during Control Period and Treated Period

| Scheduled Visit | Target Day of the Visit | Analysis Visit Window |
|-----------------------|----------------------------|---------------------------|
| Most Recent Treatment | Day 1 | Day 1 |
| Week 8 | Day 57 | Days [2, 85] |
| Week 16 | Day 113 | Days [86, 141] |
| Week 24 | Day 169 | Days [142, 211] |
| Week 36 | Day 253 | Days [212, 295] |
| Week 48 | Day 337 | Day 296 to study exit day |

Table 6-4 Effectiveness Analysis Visit Definitions for Control Group during Control Period

| Scheduled Visit | Target Day of the Visit | Analysis Visit Window |
|-------------------|----------------------------|---|
| Randomization Day | Day 1 | Day 1 |
| Week 8 | Day 57 | Days [2, 85] |
| Week 16 | Day 113 | Days [86, 141] |
| Week 24 | Day 169 | Day 142 to study exit day if the participant does not receive optional treatment, or to the day of treatment if the participant receives optional treatment |

Table 6-5 Effectiveness Analysis Visit Definitions for Control Group during Treated Period

| Scheduled Visit | Target Day of the Visit | Analysis Visit Window |
|---------------------------------|----------------------------|---------------------------|
| Most Recent Treatment | Day 1 | Day 1 |
| Week 8 Post-optional treatment | Day 57 | Days [2, 85] |
| Week 16 Post-optional treatment | Day 113 | Days [86, 141] |
| Week 24 Post-optional treatment | Day 169 | Day 142 to study exit day |

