6.4 Unscheduled Visits

An unscheduled visit may occur for safety purposes (eg, if the subject needs to obtain information regarding AEs or ISRs). An unscheduled visit may also occur to repeat facial digital images if those obtained at the scheduled visit are poor quality images. Applicable procedures will be performed and recorded on the eCRF.

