| JUVI | DEKIM | VOLC | IVIA WIL | II LIUOCAIIIC | |
|------|--------|--------|------------|----------------------------------|----|
| | | 6.3.3. | Protocol | Deviations | 25 |
| | | 6.3.4. | Medical | History | 26 |
| | | 6.3.5. | Prior/Co | ncomitant Medications | 26 |
| | | | | | |
| | | | | | |
| | | | | | |
| | | | | | |
| | | | | | |
| | | | | | |
| | 6.4. | Data H | Iandling C | Convention | 28 |
| | | | _ | Window | |
| | | | | Effectiveness | |
| | | | 6.4.1.2. | Safety | 29 |
| | | 6.4.2. | | Date Imputation | |
| | | | | Missing/Incomplete AE Start Date | |
| | | | | Missing/Incomplete AE End Date | |
| 7. | Refere | nces | | | 31 |
| | | | | | |

List of Tables

| Table 4–1 | Analysis Populations | 12 |
|-----------|--|----|
| Table 5-1 | CP and TP definition | 13 |
| Table 5–2 | Sensitivity Analyses of Primary endpoint. | 16 |
| Table 5–3 | Secondary Effectiveness Analyses | 17 |
| | | |
| Table 5–5 | Exposure to Study Treatment. | 19 |
| Table 5–6 | Administration of Study Treatment | 19 |
| Table 5-7 | TEAE Summaries | 20 |
| Table 5-8 | ISR Analyses | 21 |
| Table 5-9 | Procedural Pain Analyses | 21 |
| Table 6-1 | Protocol Deviation Summary | 26 |
| Table 6-2 | Prior and Concomitant Medications | 26 |
| Table 6-3 | Effectiveness Analysis Visit Definitions for Treatment Group during Control Period and Treated Period. | 29 |
| Table 6-4 | Effectiveness Analysis Visit Definitions for Control Group during Control Per | |
| Table 6-5 | Effectiveness Analysis Visit Definitions for Control Group during Treated Per | |
| Table 6-6 | Imputation Scenarios | 30 |

SAP Version History

This SAP for study 1894-701-008 is based on the protocol Amendment 1 (dated 22-Sep-2017).

| | SAP Version History Summary | | | | | |
|----------------|-----------------------------|---|---|--|--|--|
| SAP Version | Approval Date | Change | Rationale | | | |
| 1 | August 13, 2019 | Not Applicable | Original version | | | |
| 2 | | Baseline definition for efficacy analysis in control group | Including participants with baseline 3D photos taken after randomization due to Canfield setting-up error | | | |
| | | Add a rule of analysis for participants who have two measurements at one visit in Section 6.4.1 | Dealing with data issues: some participants have more than one photo taken at one visit | | | |
| | | Add explanation of analysis population definition change | Providing justification of the changes | | | |

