5.1. General Considerations

- The primary analysis will be performed after the database is locked and randomization schedule is released.
- Participants will receive treatment at the outset of the study (treatment group) or have treatment delayed until Week 24 (control group). The delayed treatment for control group is optional and referred to as "Optional Treatment".
- Control Period (CP), Treated Period (TP) are defined in Table 5-1.

Table 5-1 **CP and TP definition**

| Randomization | Period | Treatment | Start Date | End Date |
|---------------|--------|------------------------|---------------------------------|---|
| Group | | Group Label | | |
| Treatment | СР | VOLUMA | Initial treatment date | The date of effective assessment for Week 24. If multiple assessments fall into Week 24 window, the date of the assessment included in the Week 24 analysis will be used as end date. For participants who exit before Week 24, the end date is study exit date. For participants with intermittent missing assessment at Week 24, the target day for Week 24 (Day 169) will be the end day. |
| | TP | VOLUMA | Initial treatment date | Study exit date |
| Control | СР | Control | Randomization date | For participants who do not receive optional treatment If multiple assessments fall into Week 24 window, the date of the assessment included in the Week 24 analysis will be used as end date. For participants who exit before Week 24, the end date is study exit date. For participants with intermittent missing assessment at Week 24, the target day for Week 24 (Day 169) will be the end day. For participants who receive optional treatment: The day before optional treatment |
| | ТР | VOLUMA Post-Control | Optional initial treatment date | Study exit date |

JUVÉDERM® VOLUMA® with Lidocaine

- For CP, effectiveness analyses and baseline characteristics will be performed on the mITT population using the "as-randomized" assignment. One of the sensitivity analyses for the primary endpoint will be based on PP population. Safety analyses for CP will be conducted using the Safety Population based on "as-treated" assignment.
- For TP, effectiveness and safety summaries will be performed on the VITP and VOTP using "as-treated" assignment.
- For applicable effectiveness endpoints, baseline is defined as the last non-missing value prior to the start of study treatment for treatment group or no later than randomization date for control group.

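### SAP 6.4.1.1 ignores image quality, so a later-day repeat of a poor follow-up image is set aside whenever the poor image lies nearer the target day

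*SAP*

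**What the plan says.** Protocol 6.4 (Unscheduled Visits) gives poor images as a reason for a return visit: "An unscheduled visit may also occur to repeat facial digital images if those obtained at the scheduled visit are poor quality images".

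SAP 6.4.1.1 sets the visit windows for the effectiveness data and the rule for choosing among several measurements in a window: "the measurement that close to the target date of the visit will be used for summary analysis". Its tie-break reads: "If both measurements have the same time interval to the target date, the later one will be used for summary analysis". Measurements not chosen appear only in data listings. For the treatment group, the Week 24 target is Day 169 and the window runs from Day 142 to Day 211 (SAP Table 6-3).

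The SAP Version History says the rule was added in version 2 for this reason: "Dealing with data issues: some participants have more than one photo taken at one visit". It does not say why the extra photos were taken.

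Baseline is governed separately. SAP 5.1 takes the last non-missing value before study treatment (treatment group) or no later than the randomization date (control group).

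**The concern.** The primary endpoint is a volume change computed from these images. A return visit under Protocol 6.4 takes place because the scheduled image was thought inadequate, and the repeat is then normally on a later day. The SAP rule looks only at distance from the target day, so it can put the inadequate image back into the analysis and leave its replacement in a listing.

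At stake is avoidable measurement error at Weeks 8, 16 and 24, in the participants for whom the protocol provided a remedy. Without a stated quality rule, any later wish to use the better image would also be an unplanned choice.

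**Working it through.** **Does the rule reach the primary analysis?** The wording refers to summary analysis, but three points indicate that it does.
- It stands in the section defining the Week 8, 16 and 24 effectiveness windows. The model in SAP 5.3.2 uses those visits with an unstructured covariance within participant, so it needs one record per participant and visit.
- SAP Table 5-1 presupposes such a selection: "If multiple assessments fall into Week 24 window, the date of the assessment included in the Week 24 analysis will be used as end date".
- The SAP shows no other rule for choosing among follow-up images.

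**When is the poor image kept?** Let d be the scheduled image's day minus the target day, and r the days until the repeat. Both images are assumed to yield a volume. The poor image is kept when |d + r| > |d|; equality selects the repeat.
- Same-day repeat (r = 0): tie, so the repeat is used.
- Scheduled image on or after target (d ≥ 0) and r ≥ 1: d + r > d, so the poor image is always kept. Example at Week 24: a poor image on Day 170 is 1 day from target and a repeat on Day 177 is 8 days away, so Day 170 is analysed.
- Scheduled image k days early (d = −k): the poor image is kept only if r > 2k. A repeat within 2k days is used.

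**How often, under assumed timing?** Assume scheduled visits are spread evenly over −W to +W days. This spread is an assumption. For W = 7 there are 15 possible days, 8 of them on or after target:
- r = 1: 8/15 = 53%
- r = 3: adds k = 1, giving 9/15 = 60%
- r = 7: adds k = 1 to 3, giving 11/15 = 73%
- r = 14: adds k = 1 to 6, giving 14/15 = 93%

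The same count for other spreads gives the share of poor images kept:

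| Repeat after | W = 3 | W = 7 | W = 14 |
|---|---|---|---|
| same day | 0% | 0% | 0% |
| 1 day | 57% | 53% | 52% |
| 3 days | 71% | 60% | 55% |
| 7 days | 100% | 73% | 62% |
| 14 days | 100% | 93% | 72% |

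The latest repeat in this table is 14 + 14 = 28 days after target. That is Day 85, 141 or 197, so for the treatment group every repeat stays inside its Week 8, 16 or 24 window.

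If later-day repeats are spread evenly over 1 to 14 days, the poor image is kept in 88%, 73% and 62% of them for W = 3, 7 and 14. Among all repeats, the share falls below one half once same-day repeats exceed 1 − 0.5/0.878 = 43%, 1 − 0.5/0.733 = 32% and 1 − 0.5/0.621 = 19% respectively.

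**What could it do to power?** SAP section 3 plans 90 and 30 participants, a difference of 0.9 mL, SD 0.9 mL, 2-sided 5%, and states 99.6%. The noncentrality is 0.9 / (0.9 × √(1/90 + 1/30)) = 4.74. The noncentral t with 118 degrees of freedom gives 99.70% and the normal approximation 99.73%, close to the stated figure.

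Now suppose 20% of images in both groups carry independent extra error with SD 0.9 mL. The SD becomes √(0.81 + 0.20 × 0.81) = 0.986 mL, and power by the same normal approximation is 99.1%. The 20% and the error SD are illustrative and not taken from the documents.

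**The case against.** A distance rule with a fixed tie-break is objective and set in advance, and because all measurements are listed, any selection can be seen. It also chooses between measurements, not photographs: where the technician could derive no volume from a poor image, there is nothing to choose between. All of this stands. It limits the problem to later-day repeats where both images gave a volume.

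A reader might infer three stronger things, and the documents support none of them.
- *That the repeat is usually discarded.* This depends on visit timing, the delay to the repeat and the share of same-day retakes, none of which is given. If visits tend to be early, the rule can favour the repeat.
- *That the Version History shows poor images being reinstated.* It says only that "some participants have more than one photo taken at one visit". It mentions neither quality nor return visits, and read literally it includes same-day duplicates, which the tie-break settles in favour of the later image.
- *That the primary comparison is biased.* Bias would need poor image quality to differ between groups, and nothing in the documents suggests that it does.

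A remedy saying simply that a repeat replaces the scheduled image would also be unsafe. It could admit an image from outside the window, or, for control participants, one taken after optional treatment, which Protocol 6.2.3.2 allows within 10 days of the Week 24 visit.

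**Conclusion.** The point holds in limited form. The SAP does not carry the protocol's image-repeat provision into the choice of follow-up measurement. When a later-day repeat and the poor image both yield a volume, the poor one is analysed if it is nearer the target day, and always if the scheduled visit was on or after that day.

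Under evenly spread visits the poor image is kept in 52% to 100% of later-day repeats in the scenarios above. These figures rest on assumed timing and say nothing about how many participants are affected. The likely consequence is some added noise in a comparison with ample planned power, so the effect on the primary result is probably small. The change is still worth making, because the stated rule gives a worse measurement than the one available and correcting it is cheap.

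**What to change.** Add one sentence before the distance rule in SAP 6.4.1.1:

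> A follow-up image judged of inadequate quality, under blinding and before the randomization schedule is released, is not eligible if an adequate repeat exists within the same analysis window and, for control participants in the Control Period, before any optional treatment; the closest-to-target rule then applies among the eligible images.

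Leave the baseline rule in SAP 5.1 as it is. It already prefers the last eligible value, and extending a replacement rule to baseline could override its cut-off.

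The cost is one sentence and a quality flag. The documents describe no technician quality record, and Protocol 6.4 says only that applicable procedures go on the eCRF. The flag may therefore have to come from the blinded imaging vendor or the unscheduled-visit record. Some analysed images will lie slightly further from the target day, though still inside the window. Planned sample size and power are unaffected.

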6.4.1.2. Safety

No analysis visit windows are defined.

6.4.2. Missing Date Imputation

Missing date will be only imputed for TEAEs. Dates may be imputed with year, month, and day values under certain scenarios in Table 6-6.

JUVÉDERM® VOLUMA® with Lidocaine

Table 6-6 Imputation Scenarios

| | Complete | | | |
|----------|----------|-------|-----|-----------------|
| Scenario | Year | Month | Day | Imputable |
| 1 | Yes | Yes | Yes | Complete |
| 2 | Yes | Yes | _ | Yes |
| 3 | Yes | _ | Yes | No ^a |
| 4 | Yes | _ | _ | Yes |
| 5 | _ | Yes | Yes | No ^a |
| 6 | _ | Yes | _ | No ^a |
| 7 | | _ | Yes | No ^a |
| 8 | _ | _ | _ | Yes |

^a Not allowed per database design.

6.4.2.1. Missing/Incomplete AE Start Date

For scenario 2, i.e. if day is missing but month and year are available, then the imputed day will be the first day of the month or the initial injection date (randomization date for control group) if they have the same month and year, whichever is later (because TEAE onset is not expected prior to administration of study treatment);

For scenario 4, i.e. if day and month are missing but year is available, then the imputed day and month will be 01 Jan or the initial injection date (randomization date for control group) if they have the same year, whichever is later;

For scenario 8, i.e. if day, month and year are all missing, impute start date as the earliest possible date on or after initial injection date for treatment group. And impute start date as the earliest possible date on or after randomization date for control group.

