- Descriptive statistics for continuous variables include the sample size (n), mean, standard deviation, median, 1st and 3rd quartiles, minimum, and maximum.
- Summary statistics for categorical variables include the sample size (N1), frequency count, and percentage.
- Partial dates will be treated as missing in computations but listed in the data listings as they appear on the eCRFs unless otherwise specified. No imputation of missing values will be performed, unless otherwise specified.
- The level of significance used for all statistical tests will be 0.05, 2-sided, unless stated otherwise.
- The change from baseline values will be computed as the value for the post baseline visit minus the baseline value, unless otherwise indicated.
- All statistical analysis will be performed using SAS version 9.3 or higher.
- MedDRA will be used to code adverse events and medical history.
- WHO Drug Dictionary will be used to code medications.

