5.6.3. Adverse Events

An AE will be considered a TEAE if the AE began or worsened (increased in severity or became serious) on or after the date (and time, if known) of the initial treatment for treatment group and after randomization for control group.

An AE will be considered a TESAE if it is a TEAE that additionally meets any SAE criterion.

TEAEs will be summarized by treatment group for CP using the Safety population.

TEAEs will also be summarized for TP using VITP and VOTP, respectively.

The number and percentage of participants with TEAEs as well as the events in the following AE categories will be summarized for the above populations as described in Table 5-7.

If more than 1 AE is coded to the same preferred term for the same participant, the participant will be counted only once for that preferred term using the most severe and most related occurrence for the summarizations by severity and by relationship to study intervention.

Listings of all TEAEs, TESAEs, TEAEs leading to discontinuation, and death will be presented.

Table 5-7 TEAE Summaries

| Endpoint | Description | Timing | Methodology |
|--------------------------------|--|--------|--|
| Overall summary | Overall summary only for the following categories: TEAEs Treatment-related TEAEs Treatment-related TEAEs at injection site Treatment-related TEAEs not at injection site TESAEs Treatment-related TESAEs Treatment-related TESAEs Treatment-related TESAEs at injection site Treatment-related TESAEs not at injection site Discontinued due to TEAE Deaths | CP, TP | Categorical descriptives, event descriptives |
| TEAEs | Overall summary and by SOC and PT Overall summary and by SOC, PT, and maximum severity | CP, TP | Categorical descriptives, event descriptives |
| Treatment-related TEAEs | Overall summary and by SOC and PT Overall summary and by SOC, PT, and maximum severity Overall summary by maximum severity, time to onset, duration, action taken and outcome | CP, TP | Categorical descriptives, event descriptives |
| TESAEs | Overall summary and by SOC and PT | CP, TP | Categorical descriptives, event descriptives |
| AEs leading to discontinuation | Overall summary and by SOC and PT | CP, TP | Categorical descriptives, event descriptives |

SAP 1894-701-008 amendment 1

5.6.4. **Injection Site Response**

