6.4.2.2. Missing/Incomplete AE End Date

For scenario 2, i.e. if day is missing but month and year are available, then the imputed day will be the last day of the month or the study exit date if they have the same month and year, whichever is earlier.

For scenario 4, i.e. if day and month are missing but year is available, then the imputed day and month will be 31 Dec., or the study exit date if they have the same year, whichever is earlier

For scenario 8, i.e. if day, month and year are all missing, then the imputed date will be the latest possible date on or before study exit date.

7. References

ALLERGAN

SAP 1894-701-008 Voluma Nose China

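### SAP 6.4.2 does not confine earliest-possible AE start dates to TEAE classification, so they can distort time to onset, duration and, for treated controls, period assignment

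*SAP*

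**What the plan says.** SAP 5.1 sets the default: "Partial dates will be treated as missing in computations but listed in the data listings as they appear on the eCRFs unless otherwise specified". SAP 6.4.2 is the apparent exception: "Missing date will be only imputed for TEAEs". It does not say which summaries may use an imputed date.

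SAP 6.4.2.1 gives three start-date rules:

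- Day missing: "the imputed day will be the first day of the month or the initial injection date", the latter only if month and year match and it is later. The reason given is "because TEAE onset is not expected prior to administration of study treatment".
- Day and month missing: "the imputed day and month will be 01 Jan or the initial injection date", the latter only if the year matches and it is later.
- Wholly missing: "impute start date as the earliest possible date on or after initial injection date for treatment group".

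For controls, randomization replaces initial injection throughout. No rule mentions the touch-up or the optional treatment.

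End dates go the other way. For a wholly missing end date, SAP 6.4.2.2 says "then the imputed date will be the latest possible date on or before study exit date".

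For treatment-related TEAEs, SAP Table 5-7 plans an "Overall summary by maximum severity, time to onset, duration, action taken and outcome". The SAP gives no formula for time to onset and does not say which treatment starts the clock. SAP 5.6.4 counts ISR day from the most recent treatment, and SAP 6.4.1.1 uses most recent treatment for the effectiveness windows. SAP Table 5-1 starts the Treated Period of treated controls at optional treatment and ends their Control Period the day before.

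**The concern.** Moving an incomplete start date to the earliest possible day is a cautious way to decide TEAE status, because a doubtful event is kept in. It is not an estimate of when the event began. Measured from initial injection, every error makes onset look earlier, which is not the cautious direction when onset is the quantity being summarized. An earliest start combined with a latest end also lengthens duration.

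The anchor has a second effect. An event caused by a touch-up or by optional treatment can receive a start date before that treatment. For treated controls this can move the event between periods: it leaves the post-treatment summary and enters the Control column of the Control Period table.

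The events most exposed are probably later ones. The diary stops at 56 days after each treatment. After that, AEs depend on a general question at visits (Protocol 11.1.1), which are 8 to 12 weeks apart from Week 8 to Week 48.

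**Working it through.** The plan states no figure here, so the check applies its rules to assumed cases.

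**Do imputed dates reach the onset row?** SAP 5.1 treats partial dates as missing unless another section says otherwise. SAP 6.4.2 says otherwise for TEAEs and sets no limit on use. It also imputes end dates, which play no part in TEAE status; their evident use is duration, which stands beside time to onset in the same row of Table 5-7. The natural reading is that imputed dates feed that row. No sentence says so.

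**Inputs.** The rules are those of SAP 6.4.2.1. Touch-up is 56 to 63 days after initial treatment (Protocol synopsis, 8 (+1) weeks). Assumptions: initial injections spread evenly over one 365-day calendar year, and a fixed true onset L days after injection. Protocol 4.2 plans about 36 weeks of enrollment, so real shares depend on the calendar.

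**Shift from initial injection**

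- Wholly missing: with nothing else known, the imputed date is the injection date, so the shift is L for every event. A true day 168 or day 330 becomes day 0.
- Year only: the imputed date is the injection date if onset is in the injection year, a share of 1 − L/365. Otherwise it is 01 Jan, a mean shift of (L − 1)/2. Mean shift = L(1 − L/365) + (L/365)(L − 1)/2.
- Month only: the shift is day of month minus 1, once onset is past the injection month. The mean is (7×465 + 4×435 + 378)/365 = 5373/365 = 14.7 days, and the maximum is 30.

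| True onset L | Year only: set to day 0 | Year only: mean shift | Month only: set to day 0 |
|---|---|---|---|
| 60 | 305/365 = 84% | 55 days | 0% |
| 168 | 197/365 = 54% | 129 days | 0% |
| 330 | 35/365 = 10% | 180 days | 0% |

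**Dated before the touch-up.** Take true onset d days after touch-up. A month-only event falls before the touch-up if its day of month exceeds d + 1. A year-only event does so unless onset lies in the first d + 1 days of a new year.

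| d | Month only | Year only | Wholly missing |
|---|---|---|---|
| 3 | (365 − 48)/365 = 87% | 361/365 = 99% | 100% |
| 14 | (365 − 180)/365 = 51% | 350/365 = 96% | 100% |
| 30 | 0% | 334/365 = 92% | 100% |

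The result is the same for a touch-up at day 56 or day 63.

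**Treated controls.** The same shares give the chance that an incompletely dated event after optional treatment is imputed before it (checked at 168 and 178 days after randomization). A date before optional treatment falls in the Control Period of Table 5-1.

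**Direction depends on the clock.** Suppose the touch-up is on the 20th, 56 days after initial treatment, with a reaction two days later known only by month. It is imputed to the 1st, 19 days before the touch-up. From initial injection, onset moves from day 58 to 56 − 19 = day 37. On a most-recent-treatment clock it moves from 2 days to 37 days, so it looks more delayed.

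**The case against.** The strongest reply is that the SAP never says imputed starts enter time to onset. The default in SAP 5.1 points the other way, the only reason given in 6.4.2.1 concerns TEAE status, and table specifications are in a separate document. This stands as a limit: the point rests on the natural reading of an unrestricted rule.

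A reader might infer that late events with incomplete dates are generally reported as immediate. The rules do not support that. A late event missing only its day stays late, and a year-only event reaches the injection day only within the injection year. Even for undated events, the words about the earliest possible date could allow bounding by other information.

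A reader might also infer that touch-up reactions are counted under the wrong session. Table 5-7 has no split of AEs by session. Diary ISRs are recorded daily and summarized by session outside 6.4.2.

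Nor are delayed events hidden. All TEAEs are listed, and partial dates are listed as recorded. Counts by preferred term and severity do not depend on onset day within a period. Protocol 4.1 asks for long-term safety data but does not name acute versus delayed onset as a purpose.

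Finally, AEs are queried at each visit, recorded on awareness and source-verified, so incomplete dates may be few. All of this reduces the size of the problem. None of it makes the earliest possible date a sound onset date, and none of it answers the period problem for treated controls.

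**Conclusion.** The point holds as a minor one. On the natural reading, imputed starts and ends enter the Table 5-7 onset and duration row. For wholly undated events the onset error equals the full true lag. For year-only events it is large when onset is in the injection year. For month-only events it is at most 30 days, but enough to place most reactions in the first week after a touch-up or optional treatment before that treatment (87% at 3 days and 74% at 7 days, under an even calendar spread). The control-group anchor matters more than the onset row, because it can move an event between the untreated and treated summaries.

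The percentages rest on the assumed calendar spread and fixed onset lags. The documents do not give the number of incomplete dates, so the effect on the final tables cannot be sized. The summaries are descriptive; no test, power figure or sample size is affected.

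**What to change.** In SAP 6.4.2, state that imputed start dates are used only for TEAE status and period assignment. For controls who receive optional treatment, replace the default to randomization with assignment to a period from the known part of the date, the end date, the visit at which the event was reported and its relationship to treatment.

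In Table 5-7, compute time to onset and duration from complete dates only. Measure onset from the most recent treatment, as SAP 5.6.4 already does for ISR day. Add an 'onset date incomplete' count.

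Imputed dates then cannot enter the onset or duration figures. The cost is a few sentences and one table row. A few events move from an onset category to the 'incomplete' row, and the period rule for treated controls needs some case-by-case judgement, best recorded before database lock.
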